6.5.3 Prohibited Medicines

Any additional concomitant therapy or procedure that becomes necessary during the study and any change to concomitant drugs must be recorded in the corresponding section of the eCRF, noting the name, dose, duration, and indication of each drug.

The following are not permitted during the study:

- Any other concomitant cancer drug therapy, including chemotherapy, biological therapy, hormonal therapy for anticancer purposes, targeted therapy, or any investigational product other than tepotinib and osimertinib as defined in this protocol
- Any concomitant medication known to prolong the QT interval and cause Torsade de Pointes (refer to [Appendix 8](#))
- Drug(s), for which the package insert/SmPC includes a contraindication for P-gp (eg, dabigatran, aliskiren, colchicine), BCRP, OCT1, OCT2, MATE1, MATE2, or OATP1B1 inhibiting drugs
- Drug(s) that are known to be potent inducers of CYP3A or P-gp and thereby may decrease efficacy of osimertinib and tepotinib, including carbamazepine, phenytoin, rifampicin, and Saint John's wort.

Use of prohibited medicines for any reason must result in withdrawal of the participant from this study. For further details with regard to drug-drug interactions, refer to the tepotinib IB.

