Safety and efficacy data outputs for any interim analyses (Refer to Section 9) will be provided to the IDMC. The IDMC will give a recommendation regarding further conduct of the study. The Sponsor management will take the final decision if the IDMC recommends stopping the study. After the enrolment halt the requirements for an IDMC do no longer exist and no further IDMC meetings will be conducted.

Follow-up Period

All participants are to be followed up after stop of study intervention, including an EoT visit within 14 days since documented decision by the Investigator to permanently discontinue study intervention. A Safety Follow-up Visit will occur 30 ± 3 days after the last dose of study treatment for all participants who discontinue study intervention permanently. In case EoT Visit and Safety Follow-up Visit end up falling within the same 7 days, only EoT Visit should be performed. Participants who withdraw from the treatment for reasons other than progressive disease (PD) or death have additional visits for tumor assessments every 6 weeks until 9 months after first administration of study intervention and every 12 weeks thereafter until disease progression. Survival follow-up is to be performed every 3 months (± 2 weeks) at clinic visit or by telephone contact. Participants' survival information will be collected. Any subsequent anticancer therapy given to the participant until death should be recorded.

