4.4 End of Study Definition

A participant has completed the study if he/she has completed all study parts, including all scheduled procedures (including survival follow-up).

The end of the study is defined as the date of study intervention discontinuation by all participants (due to either disease progression, undue toxicity, or withdrawal, and, therefore, are not likely to benefit from the study intervention any longer) and two thirds of the participants have died or were followed up for at least 3 years, whatever occurs first. After the end of the study a final analysis, including an analysis of efficacy and safety, will be conducted in all participants.

5 Study Population

The criteria in Sections [5.1](#) (Inclusion Criteria) and [5.2](#) (Exclusion Criteria) are designed to enroll only participants, who are appropriate for the study; thereby, ensuring the study fulfills its objectives. All relevant medical and nonmedical conditions should be taken into consideration when deciding whether a participant is suitable for this study.

Prospective approval of protocol deviations to inclusion and exclusion criteria, also known as protocol waivers or exemptions, is not permitted.

Before performing any study assessments that are not part of the participant's routine medical care, the Investigator will confirm that the participant has provided written informed consent, as indicated in [Appendix 2](#) (Study Governance).

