6.5.2 Permitted Medicines

Any medicines that are considered necessary to protect the participant's welfare in emergencies may be given at the Investigator's discretion, regardless if it results in a protocol deviation.

The only permitted medications are the following, but restrictions may apply:

- Concomitant medications that have a narrow therapeutic window and are known to be transported by P-gp (eg, rivaroxaban, apixaban, ranolazine, talinolol, and digoxin), BCRP (eg, rosuvastatin), OCT2, MATE1, and MATE2 (eg, dofetilide and metformin), OATP1B1 and OCT1 are permitted. However, cautionary use and close monitoring of signs of changed tolerability due to potentially increased exposure is advised.

- Refer to Appendix 3 for contraceptive methods for WOCBP and female partners with childbearing potential of male study participants. Accordingly, WOCBP enrolled in the study are to use effective contraception during study intervention and for 2 months after final dose. Males and their female partners are to use effective contraception for 4 months after final dose.
- Supportive treatment, eg, bisphosphonates, agents for improving appetite, if initiated prior to study entry can continue. Change in dose/schedule on study is discouraged.
- Symptomatic treatment of brain metastasis with anticonvulsants known to have a reduced risk for drug interactions such as lamotrigine, levetiracetam, pregabalin, or valproic acid.

The Investigator will record all concomitant medications/procedures taken by the participant during the study, from the date of signature of main informed consent, in the appropriate section of the eCRF.

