7.2 Participant Discontinuation/Withdrawal from the Study

- A participant may withdraw from the study at any time, at his/her own request.
- If the participant withdraws consent for future involvement in the study, any data collected up to that point may still be used, but no future data can be generated, and any biological samples collected will be destroyed.
- A participant has the right at any time to request destruction of any biological samples taken. The Investigator must document this in the site study records.
- The participant may be withdrawn by the Investigator due to participation in another clinical study.
- The participant may be withdrawn at any time at the discretion of the Investigator for safety, behavioral, compliance, or administrative reasons.
- The Schedule of Activities specifies the data to collect at study discontinuation and follow-up, and any additional evaluations that need to be completed. The Investigator will secure the safety of the study participants and make every attempt to collect data.

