8.1 Efficacy Assessments and Procedures

Complete tumor assessment of all lesions by radiographic modality (using RECIST Version 1.1) is required. CT or MRI of the chest and abdomen (including imaging of the whole of the liver and adrenal glands), must be conducted to evaluate disease in these locations. Additional anatomical areas, such as the pelvis or other body areas in question, should be investigated in case of suspicion of presence of metastases based on signs, symptoms, biochemical results and/or non-study imaging of individual participants.

In addition, all participants must have brain imaging by MRI with IV contrast enhancement, including T2/FLAIR sequences of the brain, at Screening and at Follow-up in participants with brain metastases confirmed by IRC on the baseline brain scan. For participants who are enrolled in the study and present with brain metastasis when possible, the MRI assessment shall include Coronal 3D Gd-T1WI, Axial TSE/T2WI, Axial FLAIR, Axial T1WI, Axial Gd-T1WI, and Coronal 3D Gd-T1WI. MRI may be performed without contrast enhancement, if contrast is contraindicated. At Screening and during the Follow-up visits, if brain MRI is not clinically feasible, CT of the brain with IV contrast enhancement may be used; CT may be performed without contrast enhancement, if contrast is contraindicated.

During the follow-up, tumors will be assessed every 6 weeks (\pm 7 days) following the Cycle 1 Day 1 visit until 9 months, and every 12 weeks (\pm 14 days) thereafter according to RECIST Version 1.1, until disease progression as per Investigator, death, study withdrawal, or withdrawal of consent. Both IRC and Investigator assessments will be conducted. For participants in the randomized part of the study, verification of disease progression by IRC is required. The same method of assessment and the same technique should be used to characterize each identified and reported lesion at Baseline and during the study. Tumor assessment according to RECIST Version 1.1 at EoT Visit is requested only if last tumor assessment was performed \geq 6 weeks within the first 9 months, or \geq 12 weeks after 9 months prior to EoT Visit.

When a pleural effusion occurs as an adverse event and is punctured, cytology should be evaluated for malignancy and the results communicated to the IRC for consideration of their assessment, as outlined in the IRC charter.

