Participants who withdraw from the study intervention for reasons other than PD or death will have additional visits for tumor assessments every 6 weeks until 9 months, and every 12 weeks

thereafter. A \pm 7-days time window is permitted for these additional follow-up visits until 9 months, and \pm 14 days thereafter. Reasons for study termination should be recorded if this visit is the last visit for the participant. Recording of any new anticancer therapy will be made (a tumor assessment is mandatory before initiating the new therapy).

Survival follow-up is to be performed every 3 months \pm 2 weeks at clinic visit or by telephone contact. Participants' survival information will be collected. Recording of any new anticancer therapy will be made until death. For patient reported outcomes (PROs) (EuroQol Five Dimension Five Level Scale [EQ-5D-5L], European Organization for Research and Treatment of Cancer Quality of Life Questionnaire Core 30 [EORTC QLQ-C30] and Non-small Cell Lung Cancer Symptom Assessment Questionnaire [NSCLC-SAQ]), the questionnaires will be completed at Screening (or at Day 1 of Cycle 1 prior to any other intervention or drug intake if it was missed at Screening) and every 6 weeks from Cycle 1, Day 1 until 9 months and every 12 weeks thereafter until disease progression, death, study withdrawal, or withdrawal of consent. At all visits indicated including EoT and Safety Follow-up, every effort should be made to have the questionnaires completed by the participant prior to the initiation of any other study activities (including RECIST Version 1.1 assessments) or active treatment and prior to any contact with the Investigator.

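### Protocol 6.5.3 orders withdrawal from the study for any prohibited-medicine use, which conflicts with the scan schedule after treatment stops and with the treatment-policy estimands

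*Protocol*

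**What the plan says.** **The rule.** Protocol 6.5.3 bans four classes of medicine: other anticancer drugs, QT-prolonging drugs with Torsade risk, drugs contraindicated with certain transporter inhibitors, and potent CYP3A or P-gp inducers. It then says: "Use of prohibited medicines for any reason must result in withdrawal of the participant from this study".

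**When scans stop.** Protocol 8.1 runs tumour assessments "until disease progression as per Investigator, death, study withdrawal, or withdrawal of consent".

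**When scans continue.** Protocol 8.1 also says: "Participants who withdraw from the study intervention for reasons other than PD or death will have additional visits for tumor assessments", every 6 weeks to 9 months and every 12 weeks after that. The Synopsis (stage 6) and the Follow-up Period text of 4.1 give the same schedule and run it to progression. Section 4.1 opens that text with "All participants are to be followed up after stop of study intervention".

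**Neighbouring text.** Section 6.5.2 lets emergency medicines be given "regardless if it results in a protocol deviation". Section 6.4 says that noncompliant participants may be taken off study intervention. Section 7.1, on stopping intervention, does not list prohibited medicines. Section 7.2, on leaving the study, rules out future data only where consent is withdrawn, and otherwise asks the Investigator to "make every attempt to collect data".

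**SAP.** The estimands table in Section 14 ignores treatment discontinuation for objective response, DOR and PFS. Section 9.11 does not impute missed scans. Sections 14.2.3 and 14.2.5 censor DOR and PFS at the last evaluable scan when there is no event. Section 10.3.1 counts prohibited medication as an important protocol deviation.

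**The concern.** The protocol distinguishes leaving study intervention (7.1) from leaving the study (7.2), and 6.5.3 names the second, as an obligation and for any reason of use. Together with the stopping list in 8.1, this gives a site a literal basis for ending scans in someone who has not progressed.

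The trigger is easy to meet. The Appendix 8 examples of QT-prolonging drugs include ondansetron and azithromycin, and Protocol 2.3 names nausea and vomiting as adverse reactions to tepotinib. One short course for toxicity or infection would be enough.

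Two things are at stake. A response seen once but not confirmed at least 28 days later counts as non-response in the ORR. DOR and PFS would be censored at the last evaluable scan, and that censoring could be informative if the medicine was given for toxicity.

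**Working it through.** **1. The texts side by side.** Take a participant without progression who receives a prohibited medicine.
- Under 6.5.3 and the 8.1 stopping list, the participant is withdrawn from the study and scheduled scans end.
- Under the Synopsis, 4.1 and the later paragraph of 8.1, the same participant has stopped treatment for a reason other than progression or death, so scans continue.

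Both descriptions fit, and the protocol does not say which prevails.

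**2. The plan's own figure.** Protocol 9.2 assumes a true ORR of 50% and n = 80, and gives a 78% probability that the exact lower 95% limit exceeds 35%. The smallest qualifying count is 37 (lower limit 35.03%; 36/80 gives 33.85%). P(X ≥ 37 | n = 80, p = 0.50) = 78.3%, so the figure reproduces.

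**3. Effect per participant.** One would-be responder lost before confirmation lowers ORR by 1/80 = 1.25 points. Exact (Clopper-Pearson) lower 95% limits:
- 40/80: 38.6%
- 39/80: 37.4%
- 38/80: 36.2%
- 37/80: 35.0%
- 36/80: 33.9%

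From 40/80, four losses are needed to fall below 35%.

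**4. Effect on the planning probability (illustration only).** Let f be the share of participants withdrawn under the rule and L the share of their would-be responses left unconfirmed. Neither is in the documents. Then p = 0.50 × (1 − fL):
- f = 2.5%, L = 25%: p = 0.497, probability 76.6%
- f = 2.5%, L = 50%: p = 0.494, probability 74.9%
- f = 5%, L = 50%: p = 0.4875, probability 71.2%
- f = 10%, L = 50%: p = 0.475, probability 63.1%

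**5. How far the EoT scan helps.** Section 8.1 says: "Tumor assessment according to RECIST Version 1.1 at EoT Visit is requested only if last tumor assessment was performed" at least 6 weeks earlier (first 9 months). The EoT Visit falls within 14 days of the decision to stop. Assume that the visit takes place and that the decision time u is uniform over the 42 days after a first-response scan, with visit delay d. A scan is requested if u + d ≥ 42, so the share confirmed is d/42:
- d = 0: 0%
- d = 14: 14/42 = 33%
- d uniform on 0 to 14: 7/42 = 17%
- next scan at its latest permitted day (42 + 7 = 49), d = 14: 21/49 = 43%

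**6. What remained open at SAP v4.0 (04 April 2023).** SAP Section 7 dates the last global treatment start at 28 June 2022. Two 6-weekly scans (84 days) take that to 20 September 2022, and 9 months take it to about 28 March 2023, the latest trigger date for the primary analysis under SAP 6.3. Both precede SAP v4.0. The Chinese extension, enrolled to 7 November 2022, is outside the primary efficacy analysis. The final analysis is at most 3 years after the last first dose. If that dose was close to 7 November 2022, the limit is about 7 November 2025: 948 days, or 948/30.4375 = 31.1 months, after SAP v4.0. This is an upper bound, because the study ends sooner if all have stopped treatment and two thirds have died.

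**The case against.** The best defence is that 6.5.3 is loose wording and that the rest of the protocol shows the intent. This has force. The Synopsis and 4.1 give the full schedule to progression, with no exception for study withdrawal. Section 7.2 closes off new data only on withdrawal of consent, and the Schedule of Activities marks tumour assessment under additional follow-up. Section 8.1 requires a scan before any new anticancer therapy, which covers the first banned class. SAP Section 9 uses unscheduled visits in deriving efficacy endpoints, so an extra scan would count, and the EoT condition does not forbid an earlier one. These points make loss of scans a possibility and not a certainty. They do not remove the conflict, because sites work from the written rule and it names the study.

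A reader might infer two stronger points that the documents do not support.
- *Overall survival follow-up is cut off.* Nothing says so. The Synopsis, 4.1 and 8.1 set survival contact every 3 months without a study-withdrawal stop. Section 4.4 only defines when a participant has completed the study, and the SAP 10.1 categories are disposition counts.
- *The primary ORR is biased.* No rate of use is given and no participant is shown to have been affected. The 35% value is a planning benchmark, since Protocol 9.1 tests no formal hypothesis, and an amendment after SAP v4.0 could not change the primary result.

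**Conclusion.** The conflict is real and the point is minor. Read literally, 6.5.3 and the stopping list in 8.1 can end scans that other sections schedule and that the estimands for response, DOR and PFS rely on. The effect on ORR is confined to responses not yet confirmed; those already confirmed stand. The 40/80 starting point, the shares f and L, and the uniform timing are assumptions used to show scale, and they do not estimate what happened. The effect on DOR and PFS is not quantified; the 31 months bounds only the calendar time in which it could arise.

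**What to change.** In 6.5.3, replace the required withdrawal from the study with: *discontinuation of study intervention; tumour assessments per 8.1 and survival follow-up continue unless consent is withdrawn*. The participant then stays in the study, so the study-withdrawal stop in 8.1 is not triggered and needs no edit. Keep all four bans. Add one clause saying whether a participant given an emergency medicine under 6.5.2 may stay on study intervention, with the use recorded as a protocol deviation.

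If the rule has already been applied, report how many participants were withdrawn from the study under it before a confirmatory scan, and how many before progression. Only this timing split is new, because SAP 10.1 and 10.3.1 already plan discontinuations by primary reason and important-deviation tables and listings.

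The cost is a short edit in the next amendment, with the IRB/IEC approval that Appendix 2 requires, and two counts in the report. It uses visits already scheduled.

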6.5.4 Other Interventions

Participants may receive palliative radiotherapy, eg, for painful bone metastasis. However, the use of any localized radiation therapy during the study should be discussed with the Sponsor (or delegate) on a case-by-case basis considering the influence on imaging assessments of target/non-target lesions.

6.6

Dose Selection and Modification

Participants assigned to the combination of tepotinib plus osimertinib will take tepotinib at the assigned dose and dose regimen (dose for the overall study confirmed by SMC after the safety-run in) together with osimertinib at the approved dose of 80 mg, orally once daily, approximately at the same time (\pm 2 hours), preferentially each morning immediately after food intake with a full glass of water (approximately 200 mL).

Participants assigned to the tepotinib monotherapy treatment will take tepotinib at the 500 mg once daily dose (as currently used in the Phase II single agent VISION study), approximately at the same time (\pm 2 hours), preferentially each morning immediately after food intake with a full glass of water (approximately 200 mL).

The dose of 500 mg tepotinib once daily is the labeled dose of tepotinib in US and Japan for patients with NSCLC with METex 14 skipping alterations. The proposed administered dose of 500 mg tepotinib corresponds to 500 mg tepotinib hydrochloride hydrate and is equivalent to 450 mg tepotinib (free base form). The 250 mg tepotinib corresponds to 250 mg tepotinib hydrochloride hydrate and is equivalent to 225 mg tepotinib (free base form).

Participants will be instructed to swallow the tablets whole and to avoid biting or breaking the tablets or attempting to dissolve them in water before taking the dose.

Refer to Section [5.3](#) for food restrictions prior to PK sampling.

If a participant misses taking a scheduled dose of study drug, within a window of 12 hours, it is acceptable to take the dose. If it is more than 12 hours after the scheduled dose time, the missed dose should not be taken, and participants should be instructed to take the next dose at the next scheduled time.

If a participant vomits after taking their study drug, they should not make up for this dose, but should take the next scheduled dose.

If intolerable toxicities are observed and judged by Investigator to be related to either or both components of the study combination intervention, dose reduction of either or both components will be permitted, if criteria for participant withdrawal from study intervention have not been met. Thereby, the Investigator should notify the Sponsor (or delegate) immediately and each case should be discussed including the reason for dose reduction.

In case a dose reduction is necessary, the study intervention will be administered as follows:

If there is a Grade 3 or higher AE related to either or both components of the combination intervention, dose interruption of either or both components will be permitted for up to 3 weeks. If this AE is not recovered to Grade \leq 2 or baseline values after 3 weeks of interruption, the participant may have to permanently discontinue osimertinib, tepotinib, or both drugs. If this AE recovered to Grade \leq 2 or baseline values in less than 3 weeks, continuation of intervention can be restarted at the same dose or at a lower dose of the respective study interventions. In case of osimertinib, a lower dose of 40 mg is available. In case of tepotinib, depending on the RP2D, a reduction to 250 mg or change in dose regimen is possible. The Investigator is also permitted to reduce the dose of osimertinib and tepotinib for AEs that he/she deem related to the intervention

but is also allowed to escalate back again if the clinical condition allows. Immediate notification of the Sponsor (or delegate) is mandatory.

Further guidance on dose modification of osimertinib is given in [Table 3](#), following information as provided in the Tagrisso EU SmPC dated 28 August 2018. Since this table only provides a snapshot of current available knowledge the Investigator is advised to consider any update of osimertinib information given in respective SmPC revisions.

Table 3 **Recommended Dose Modifications for Tepotinib and Osimertinib**

Target organ	Adverse reaction ^a	Dose modification
Pulmonary	ILD/Pneumonitis.	Permanently discontinue osimertinib and tepotinib.
Cardiac	QTc interval greater than 500 ms on at least 2 separate ECGs.	Withhold osimertinib until QTc interval is less than 481 ms or recovery to baseline if baseline QTc is greater than or equal to 481 ms, then resume at the reduced 40 mg dose.
	QTc interval prolongation with signs/symptoms of serious arrhythmia.	Permanently discontinue osimertinib ^b
	Symptomatic congestive heart failure	Permanently discontinue osimertinib ^b
Body	Edema Grade 1 or 2	Dose level of tepotinib can be maintained
	Edema Grade 3	The dose of tepotinib must be interrupted until edema recovers to ≤ Grade 2 or baseline but for no more than 21 days. After recovery the patient can restart at the same dose or at 250 mg daily. If edema Grade 3 reoccurs the tepotinib dose must be interrupted again until edema recovers to ≤ Grade 2 or baseline but for no more than 21 days. After recovery, tepotinib must then be dose reduced to 250 mg daily (if the previous dose was 500 mg daily). If edema Grade 3 reoccurs at 250 mg dose, tepotinib must be permanently discontinued.
	Generalized edema Grade 4	Permanently discontinue tepotinib
	Pancreas	See detailed instruction in Section 6.8 .
Other	Any other adverse reaction of Grade ≥3	The dose of tepotinib must be interrupted until event resolves to ≤ Grade 2 or baseline but for no more than 21 days. After recovery, tepotinib may be restarted at 1 dose level below: 250 mg daily.

ECG: electrocardiogram; ILD: interstitial lung disease.

a Adverse reactions graded by NCI CTCAE v5.0

b In the case of permanent discontinuation of tepotinib or osimertinib due to toxicity, participants must permanently discontinue study treatment.

Any clinical circumstances leading to dose modifications and which are not covered by above criteria may be grounds for dose reductions or intervention interruptions and should be discussed with the Sponsor on a case-by-case basis.

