2.3 Benefit/Risk Assessment

Clinical efficacy and safety information for the use of MET inhibitors in combination with EGFR inhibitors is available from several studies. This includes information for tepotinib with the

1st generation EGFR TKI gefitinib, osimertinib with a selective MET inhibitor, savolitinib, and a head-to-head comparison between osimertinib and the 1st generation EGFR TKIs, gefitinib and erlotinib, which have been approved for decades (approved in the US in May 2003) and have been shown to be safe in patients with NSCLC.

The use of tepotinib in combination with gefitinib has already been investigated in patients with advanced NSCLC after failure of previous EGFR TKI treatment (NCT01982955, [Cheng 2018](#)). In particular, the subgroup of participants with MET amplified, T790M negative tumors, demonstrated positive efficacy signals including an ORR of 67% and a median PFS of 16.6 months were seen. Furthermore, 60 participants were exposed to tepotinib with the EGFR inhibitor. While all participants receiving this treatment experienced treatment-emergent adverse events (TEAEs), the majority of these TEAEs were mild or moderate. A comparison of tepotinib plus gefitinib versus chemotherapy showed 9.7% versus 4.3% having TEAEs leading to permanent discontinuation, 3.2% versus 0% of TEAEs leading to death (none of the TEAEs was related), 16.1% versus 30.4% had serious related TEAEs, 51.6% versus 52.2% had Grade ≥ 3 related TEAEs, and 12.9% versus 8.7% had lipase/amylase increase Grade ≥ 3 not accompanied by pancreatitis or respective symptoms. Overall, tepotinib in combination with gefitinib was considered safe and well tolerated ([Cheng 2018](#)).

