6.8 Special Precautions

The study will be performed at a clinical research site with personnel trained in basic or immediate life support. Equipment and other agents (epinephrine and prednisolone equivalents, etc.) will be available at the site in case of allergic reactions. In case of localized radiation therapy this should be discussed with the Sponsor (or delegate) on a case-by-case basis.

6.9 Management of Specific Adverse Events, Adverse Events of Special Interest or Adverse Drug Reactions

Tepotinib

Specific Adverse Events

Interstitial Lung Disease

Interstitial lung disease or ILD-like adverse reactions have been reported in the clinical study program with tepotinib in patients with NSCLC.

Participants should be monitored for pulmonary symptoms indicative for ILD or ILD-like reactions. Tepotinib should be withheld and participants should be promptly investigated for alternative diagnosis or specific etiology of ILD. Tepotinib must be permanently discontinued if ILD is confirmed and the participant be treated appropriately.

Edema

Edema has been reported frequently in the study program. It is an identified risk for treatment with tepotinib. Other AEs related to fluid retention, such as generalized edema and pleural effusion have been observed. To gain further information to the occurrence and resolution of edema, any AEs of edema, the current edema status or AE resolution is to be specifically documented at each visit.

In the case of edema, please follow the advice provided in Table 3 in Section [6.6](#).

Asymptomatic Pancreatic Enzyme Elevation

If an asymptomatic lipase/amylase elevation of Grade ≥ 3 occurs, the participant will undergo clinical evaluation for the presence of signs and symptoms typical of acute pancreatitis and for

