other risk factors for pancreatitis. In addition, a computed tomography (CT) scan and/or magnetic resonance imaging (MRI) of the abdomen will be performed to assess the pancreas. The Sponsor (or delegate) will be notified of the outcome of the CT/MRI. Dosing with study treatment can continue during the evaluation period unless the clinical evaluation indicates pancreatitis. If there is no clinical or radiological evidence of pancreatitis, treatment with tepotinib should be continued, particularly if there is a potentially positive benefit for the individual participant. However, the continuation of study treatment for the participant will be individually discussed with the Investigator on a participant by participant basis.

In case of dose reduction (Section 6.6), the Investigator should notify the Sponsor immediately and each case should be discussed on a case-by-case basis, providing the reason for dose reduction.

For further information on tepotinib please refer to the tepotinib IB.

Adverse Event of Special Interest (AESI)

Adverse events suggestive of drug-induced liver injury including hepatic/liver failure and hepatitis (non-infectious) are considered AEs of special interest (AESIs) and will be reported to the Sponsor (or delegate) in an expedited fashion (refer to Section 8.3).

Osimertinib

For information on osimertinib please refer to the osimertinib prescribing information.

7 Discontinuation of Study Intervention and Participant Discontinuation/Withdrawal

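### The Pancreas row of Table 3 points to Section 6.8, which has no pancreatic instructions; they are in Section 6.9, and the texts a site might use instead differ from it.

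*Protocol*

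**What the plan says.** Table 3 in protocol Section 6.6 lists dose modifications by target organ. Its Pancreas row, as it can be read, gives no action of its own, only "See detailed instruction in Section 6.8".

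The section of that number is "6.8 Special Precautions". It deals with life-support training, equipment for allergic reactions and radiotherapy, and closes: "In case of localized radiation therapy this should be discussed with the Sponsor (or delegate) on a case-by-case basis".

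The pancreatic text is in Section 6.9, under its own subheading: "If an asymptomatic lipase/amylase elevation of Grade ≥ 3 occurs, the participant will undergo clinical evaluation". Abdominal CT and/or MRI follows, and the Sponsor is told the result. On dosing, 6.9 says: "Dosing with study treatment can continue during the evaluation period unless the clinical evaluation indicates pancreatitis". It then adds: "If there is no clinical or radiological evidence of pancreatitis, treatment with tepotinib should be continued", subject to individual discussion of each participant.

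Two other passages in 6.6 deal with Grade 3 or higher events in general. The last row of Table 3, for any other adverse reaction of that grade, says: "The dose of tepotinib must be interrupted until event resolves to ≤ Grade 2 or baseline but for no more than 21 days", with a possible restart at 250 mg daily. The body text before the table permits interruption for a related event for up to 3 weeks, with restart at the same or a lower dose.

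**The concern.** Table 3 is what a site would open when a laboratory result calls for a dosing decision. For this organ the pointer is the only instruction that can be read, and it leads to a section on a different subject. Lipase and amylase are protocol-required tests (Appendix 5), and Section 2.3 lists their increase among the adverse reactions to tepotinib, so the row will foreseeably be used.

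A site that finds nothing in 6.8 has to look elsewhere. Two of the places it might look, both within 6.6, differ from 6.9 on whether dosing is interrupted. The same laboratory finding could therefore be handled differently at different sites. There is also a consequence for the analysis: SAP Section 10.3.1 counts dose modifications that depart from the protocol among the important protocol deviations, and such departures are hard to classify until it is clear which passage governs.

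**Working it through.** No arithmetic applies. The check sets the passages side by side for one case: an asymptomatic lipase or amylase elevation of Grade 3 or higher.

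| Place in the protocol | What it gives for this case |
|---|---|
| 6.6, Table 3, Pancreas row | Only a pointer to 6.8 |
| 6.8 | Nothing on pancreas, lipase or amylase |
| 6.9 | Clinical evaluation, abdominal CT and/or MRI, Sponsor notification; dosing can go on during evaluation unless pancreatitis is indicated |
| 6.6, Table 3, last row | Interruption required, at most 21 days; restart possible at 250 mg daily |
| 6.6, body text | Interruption permitted for up to 3 weeks; restart at the same or a lower dose |

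1. *Is the pointer wrong, or only misread?* The section number in the row is legible. The table of contents gives 6.8 and 6.9 the same titles as the body. The row may have lost a cell when the PDF was read, because the organ name sits in the adverse-reaction column. A lost grade or event description would not change where the pointer leads.

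2. *Does another link repair it from within the table?* No. For edema, 6.9 sends the reader to Table 3, where edema instructions exist. For the pancreas, 6.9 refers back to 6.6 only for dose reduction, and the Pancreas row of 6.6 goes to 6.8. Nothing legible in Table 3 leads to 6.9.

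3. *Do the fallback texts agree with 6.9?* No. On interruption, the last row requires it, the body text permits it, and 6.9 lets dosing go on during the evaluation. The two texts in 6.6 also differ on the restart dose. Their time limits agree: 3 weeks is 3 × 7 = 21 days.

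4. *Does the last row apply by its own wording?* Not directly. It is for other reactions, and the pancreas has its own row. The difference becomes practical only if a site falls back on that row after finding nothing in 6.8.

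**The case against.** The strongest reply is that this is a wrong section number and little more. Sections 6.8 and 6.9 start on the same page in the table of contents, 6.8 is three sentences long, and the next section has a subheading naming pancreatic enzyme elevation. Section 8.3.3 independently sends investigators to 6.9 for monitoring and management of adverse events. Directly below Table 3, circumstances that its criteria do not cover are referred to the Sponsor case by case, and a dose reduction has to be notified to the Sponsor anyway. All of this stands. It makes mishandling less likely, but it does not make the reference correct.

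A reader might infer three stronger things, which the documents do not support:

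- *That Table 3 as printed orders an interruption which 6.9 contradicts.* As printed, the row leads to 6.8. The interrupting row is reached only by fallback, and 6.9 is not a flat rule to continue, since it calls for individual discussion.
- *That the pancreatic work-up would be skipped.* The evaluation and imaging in 6.9 do not depend on Table 3, and interrupting tepotinib does not cancel them.
- *That Sections 7.1 and 6.9 conflict.* Section 7.1 requires the Investigator to consider discontinuation for elevation with signs and symptoms suggestive of pancreatitis, or for confirmed pancreatitis. Section 6.9 concerns asymptomatic elevation and allows dosing during evaluation only while pancreatitis is not indicated. The two are compatible.

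**Conclusion.** The cross-reference is wrong, and the concern holds as an internal inconsistency in an operative safety table. It is more than a slip in background text, because the pointer is the only instruction legible in the row. The wider divergence between Table 3, the 6.6 body text and 6.9 is real on the page, but it matters in practice only if a site falls back after following the wrong pointer. The safeguards above limit that risk.

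No number of affected participants can be given. It is tempting to apply the figure in Section 2.3 for tepotinib plus gefitinib against chemotherapy: "12.9% versus 8.7% had lipase/amylase increase Grade ≥ 3 not accompanied by pancreatitis or respective symptoms". That would count expected enzyme elevations, not mishandled ones, and the figure comes from a different combination. Its denominator is not stated either: 60 participants are described as exposed, but 0.129 × 60 = 7.74 is not a whole number, and neither 7/60 = 11.7% nor 8/60 = 13.3% matches.

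The conclusion assumes that no text lost from the Pancreas row supplies a second, correct reference or an action. It takes no view on which dosing rule is right.

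**What to change.** - In the Pancreas row of Table 3, change the cross-reference from Section 6.8 to Section 6.9.
- Reconcile Table 3 and the body text of Section 6.6 with Section 6.9, so that one passage clearly governs lipase or amylase elevation of Grade 3 or higher. The sponsor decides which action applies.

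The cost is one corrected section number and a clarifying sentence, issued by clarification letter or at the next amendment. No change to the design, the sample size or the analysis is needed.
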